10.4 DESCRIPTION OF STATISTICAL METHODS

10.4.1 GENERAL APPROACH

After data set compilation and cleaning, a series of descriptive statistics will first be generated to examine the data set for distributional/potential missing data patterns and sample characteristics. The study team will conduct a series of pooled time series analyses with generalized estimating equations regression (GEE) models.³ These types of non-parametric (i.e., not based on normal distribution assumptions) predictive modeling procedures are capable of using both robust and standard estimating functions to more fully evaluate the influence RF/PEMF treatments and other factors/covariates on serial face gross elasticity measurements. These types of procedures will also enable the study team to examine the potential effects of both *within group* (e.g., face gross elasticity measurements for Patient X at three measurement points) and *between group* (e.g., face gross elasticity measurement changes of younger women versus older women) model variables. A *P*-value of <0.05 will be considered statistically significant.

10.4.2 ANALYSIS OF THE PRIMARY EFFICACY ENDPOINT(S)

Gross elasticity as measured by the Cutometer® is a ratio expressed as a percentage. Baseline and post-treatment measurements will be taken and analyzed using analysis of variance (ANOVA).

Results will be reported as baseline means with standard deviation, post-treatment means with standard deviation, and individual change for each subject.

Subjects with missing data, non-adherence, or lost to follow-up will not be included in the final analysis dataset.

10.4.3 ANALYSIS OF THE SECONDARY ENDPOINT(S)

Secondary endpoint #1: The FWES is based on an ordinal scale (from 1-9) and will be measured as a single endpoint.

Secondary endpoint #2: The GAIS is a 7-point (-3 to 3) ordinal scale and will be a repeated measure.

Secondary endpoint #3: The subject satisfaction score is a 5-point Likert scale and will be a repeated measure.

10.4.4 SAFETY ANALYSES

There are no formal safety endpoints in this study, however all AEs and relevant information related to the incidents (start date, stop date, severity, relationship, outcome, and duration) will be recorded and reported. Adverse events leading to premature discontinuation from the study and serious treatment emergent AEs will be presented in a table.

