5.4 PARTICIPANT WITHDRAWAL OR TERMINATION

5.4.1 REASONS FOR WITHDRAWAL OR TERMINATION

Subjects are free to withdraw from participation in the study without prejudice at any time upon request. In the event that a subject drops out of the study or is withdrawn from the study, the Exit/Termination CRF form should be completed. On the withdrawal page, the Investigator should record the date of the withdrawal, the person who initiated withdrawal and the reason for withdrawal.

Reasonable effort will be made to contact any subject lost to follow up during the course of the study in order to complete assessments and retrieve any outstanding data and study medication/supplies. The records of subjects who terminate prior to completing the study will be retained and the reason for termination will be documented.

An investigator may terminate participation in the study if:

- Any clinical adverse event (AE), laboratory abnormality, or other medical condition or situation occurs such that continued participation in the study would not be in the best interest of the participant.
- The subject meets an exclusion criterion (either newly developed or not previously recognized) that precludes further study participation.

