5.4.2 HANDLING OF PARTICIPANT WITHDRAWALS OR TERMINATION

Every effort will be made to continue follow-up of withdrawn or terminated subjects or subjects who discontinue the intervention but remain in the study for follow-up, especially for safety and efficacy study endpoints. Every effort will be made to undertake protocol-specified safety follow-up procedures to capture AEs, serious adverse events (SAEs), and unanticipated problems (UPs). Subjects that withdraw will be replaced until a maximum of 60 subjects are randomized with 45 subjects expected to complete the study. Subjects that withdraw or are terminated from the study will still be requested to complete the week 20 follow-up procedure in order to evaluate for possible AEs or unanticipated problems (UPs).

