8.3 TIME PERIOD AND FREQUENCY FOR EVENT ASSESSMENT AND FOLLOW-UP

The occurrence of an AE or SAE may come to the attention of study personnel during study visits and interviews of a study participant presenting for medical care, or upon review by a study monitor.

All AEs including local and systemic reactions not meeting the criteria for SAEs will be captured on the appropriate CRF. Information to be collected includes event description, time of onset, clinician's assessment of severity, relationship to study product (assessed only by those with the training and authority to make a diagnosis), and time of resolution/stabilization of the event. All AEs occurring while on study must be documented appropriately regardless of relationship. All AEs will be followed to adequate resolution.

Any medical condition that is present at the time that the participant is screened will be considered as baseline and not reported as an AE. However, if the study participant's condition deteriorates at any time during the study, it will be recorded as an AE. UPs will be recorded in the data collection system throughout the study.

Changes in the severity of an AE will be documented to allow an assessment of the duration of the event at each level of severity to be performed. AEs characterized as intermittent require documentation of onset and duration of each episode.

The PI will record all reportable events with start dates occurring any time after informed consent is obtained until 7 (for non-serious AEs) or 30 days (for SAEs) after the last day of study participation. At each study visit, the investigator will inquire about the occurrence of AE/SAEs since the last visit. Events will be followed for outcome information until resolution or stabilization.

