8.4 REPORTING PROCEDURES

8.4.1 ADVERSE EVENT REPORTING

All AEs will be recorded on the appropriate CRF and will include information about the start and stop dates, severity and relatedness. There should be an attempt to report a “diagnosis” rather than the individual signs, symptoms and abnormal laboratory values associated with the diagnosis. However, a diagnosis should be reported only if, in the Investigator’s judgment, it is relatively certain (i.e., definite or possible). Otherwise individual signs, symptoms and abnormal laboratory values should be reported as distinct adverse events.

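### The planned adverse event table may not show non-serious events that permanently stop RF/PEMF in women who stay in follow-up, and no named field marks them as the reason for stopping

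*Combined protocol and SAP*

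**What the plan says.** Section 10.4.4 makes two commitments. The first is general: "all AEs and relevant information related to the incidents (start date, stop date, severity, relationship, outcome, and duration) will be recorded and reported". The second defines the one AE table: "Adverse events leading to premature discontinuation from the study and serious treatment emergent AEs will be presented in a table". The table therefore has two categories, study discontinuation and seriousness.

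Section 5.4.2 treats stopping the device and leaving the study as different things. Its follow-up effort extends to "subjects who discontinue the intervention but remain in the study for follow-up, especially for safety and efficacy study endpoints". It also covers those who do leave: "Subjects that withdraw or are terminated from the study will still be requested to complete the week 20 follow-up procedure".

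Section 5.4.1 describes stopping because of an AE only as an end to participation ("An investigator may terminate participation in the study if"). It ties the exit form to the same event: "In the event that a subject drops out of the study or is withdrawn from the study, the Exit/Termination CRF form should be completed".

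On AE data, 8.3 begins its list with "Information to be collected includes event description, time of onset" and continues with severity, relationship and resolution. Section 8.4.1 says the form "will include information about the start and stop dates, severity and relatedness". Neither names the action taken with treatment. Section 10.4.5 plans no adherence or retention analysis, and 10.3 sets a single dataset limited to women who completed all treatment and follow-up.

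**The concern.** How many women had to give up the device because of a reaction is a basic tolerability result for an elective cosmetic treatment. The reactions that 8.2.3 lists as expected (burn, blistering and persistent erythema among them) need not meet the seriousness definition in 8.1.2, so the serious-event category cannot be relied on to catch them. That leaves the discontinuation category, which is worded at study level.

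If that wording is applied literally, the table depends on retention as well as on harm. The better the follow-up effort in 5.4.2 succeeds, the fewer treatment-stopping events the table shows. A low count could mean good tolerability, or good retention of women who could not tolerate treatment, and a reader could not tell which.

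**Working it through.** The plan states no figure on this point, so there is nothing to reproduce. The check is a reading of the sections against each other, followed by an illustration on assumed rates.

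**Step 1. Apply 10.4.4 literally to four cases.**

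| Case | Tabulated? |
|---|---|
| Non-serious AE; she leaves the study | Yes, as a discontinuation |
| Non-serious AE; she permanently stops RF/PEMF and stays in follow-up | Neither category, on a literal reading |
| Serious treatment-emergent AE, whether she stays or leaves | Yes, as serious |
| Non-serious AE; she continues treatment | No, and properly so |

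Only the second case is a problem.

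**Step 2. Look for another output that would show the second case as treatment-limiting.**

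- AE attributes in 8.3, 8.4.1 and 10.4.4: dates, severity, relationship, outcome and duration. Action taken is not named.
- Exit form (5.4.1): records who initiated withdrawal and why, but as a withdrawal from the study.
- Week 20 termination form (7.3.4): completed at the final visit, with no stated item on why treatment stopped earlier.
- Early termination visit (7.3.5): records a reason, again for ending the study early.
- Adherence and retention (10.4.5): no analysis.
- Individual listings by time point (10.4.10): could show that sessions were missed, but not why.

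None is stated to link the event to the end of treatment.

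**Step 3. Check which women the table covers.** Section 10.4.4 names no population and 10.3 allows one dataset, completers only. If that dataset also governs safety, a woman who stopped treatment early is outside it whether she stayed or left. The discontinuation category would then be empty by construction, and rewording it would not help. The documents do not say whether 10.3 applies to safety.

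**Step 4. Illustrate the possible range.** Let N be the number of women, p the proportion who stop treatment for a non-serious AE, and s the share of those who stay in follow-up. On the literal reading, leaving the Step 3 question aside:

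- expected stops = N × p
- stops shown in the table = N × p × (1 − s)

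N = 45 (expected completers) and N = 60 (the cap) come from 5.4.2. Both p and s are assumptions. With p = 5%:

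| N | Expected stops | Shown, s = 0 | Shown, s = 50% | Shown, s = 100% |
|---|---|---|---|---|
| 45 | 45 × 0.05 = 2.25 | 2.25 | 1.125 | 0 |
| 60 | 60 × 0.05 = 3.0 | 3.0 | 1.5 | 0 |

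For p from 2% to 15%, expected stops run from 0.9 to 6.75 with N = 45 and from 1.2 to 9.0 with N = 60. At p = 5% the chance of at least one such stop is 1 − 0.95^45 = 0.90 or 1 − 0.95^60 = 0.95. The case is therefore likely to arise if stops are about that frequent, but the documents do not say that they are.

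**The case against.** The strongest reply is that the second case may never arise as described. The only AE-driven stopping route in 5.4.1 ends study participation, and women who withdraw or are terminated are still asked to attend Week 20 (5.4.2 and 7.3.5). Attendance at Week 20 therefore does not show that a woman is still in the study. A site could class her as discontinued from the study, and her event would then be tabulated. This stands: the omission is possible, not certain. It also shows that the count turns on a term the plan does not define.

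A reader might infer that treatment-stopping harm disappears from the report. The documents do not support that. Serious events are tabulated whether or not the woman stays, every AE is to be reported with severity, relationship and outcome, and burns also trigger rapid reports under 7.8. Pain and local tolerability are assessed after every session. What may be missing is the identification of an event as the reason treatment ended.

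A reader might also infer that the forms cannot capture the reason. That goes too far. The list in 8.3 is open-ended, the forms themselves are not in the documents, and the termination form is also completed at Week 20. The defensible statement is that no such field is named.

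Nor does the instruction in 7.3.2 that treatment may be halted for discomfort predict permanent stops; it concerns management within a session. Finally, the study has no formal safety endpoint and no decision rule that uses this table. That limits the consequence to the completeness of the safety report.

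**Conclusion.** The point holds as a reporting gap. Under a literal reading of 10.4.4, a non-serious AE that permanently stops RF/PEMF in a woman who stays in follow-up may be absent from the table, and no named field or planned summary would identify it as treatment-limiting.

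The conclusion rests on two assumptions: that study discontinuation in 10.4.4 means leaving the study rather than stopping treatment, and that the AE form holds no more than the fields named in the text. If either is wrong, the gap narrows or closes.

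A reader might go on to infer that treatment-limiting harm will be understated by a given amount. The documents do not support that: the shortfall could be anything from none to all such stops, and the counts in the working are illustrations only. The primary analysis is not affected. The change is still worth making, ideally before the AE form is final, because a reason not recorded when treatment stops may not be recoverable later.

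**What to change.** 1. In 10.4.4, tabulate AEs leading to permanent discontinuation of study treatment and AEs leading to withdrawal from the study as separate rows or columns, and define both terms.
2. Add a field to the AE form for the action taken with study treatment, for example none, energy reduced, session halted or permanently stopped.
3. Record the reason when treatment is permanently stopped, as well as at exit from the study.
4. State that safety tables include every woman who received at least one treatment, not only the completers dataset in 10.3. Without this, the new row could still be empty.

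The cost is a few sentences in 10.4.4, one field on the AE form and one further occasion for recording a reason. The downside is that the reported number of AE-related discontinuations may be higher. This changes reporting only; it proposes no clinical stopping rule.

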10.4.5 ADHERENCE AND RETENTION ANALYSES

Not applicable.

10.4.6 BASELINE DESCRIPTIVE STATISTICS

Baseline characteristics including age, Fitzpatrick skin type, and initial Cutometer® readings will be reported using descriptive statistics.

10.4.7 PLANNED INTERIM ANALYSES

10.4.7.1 SAFETY REVIEW

Not applicable.

10.4.7.2 EFFICACY REVIEW

Not applicable.

10.4.8 ADDITIONAL SUB-GROUP ANALYSES

For all endpoints, additional sub-group analysis may be performed based on age group and Fitzpatrick skin type.

10.4.9 MULTIPLE COMPARISON/MULTIPLICITY

Not applicable

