10.2 STATISTICAL HYPOTHESES

Statistical null hypothesis for primary endpoint: there will be no statistical change in gross elasticity as measured by the Cutometer[®] after treatment with combined RF/PEMF compared to before treatment.

Statistical null hypothesis for secondary endpoint #1: there will be no statistical change in the FWES as rated by blinded clinicians after treatment with combined RF/PEMF compared to before treatment.

Statistical null hypothesis for secondary endpoint #2: there will be no statistical change in the GAIS as rated by the subjects after treatment with combined RF/PEMF compared to before treatment.

Statistical null hypothesis for secondary endpoint #3: there will be no statistical change in the subject satisfaction score after treatment with combined RF/PEMF compared to before treatment.

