10.5 SAMPLE SIZE

The PI has used G*Power 3.10.10 software⁴ to generate *a priori* minimal sample size calculations for the primary study endpoint: changes in *gross elasticity* (GE) repeated measure face measurement in a sample of consented eligible women at three time points: a) prior to RF/PEMF, b) at time of RF/PEMF completion, and c) three months after treatment completion.

These calculations indicate that a minimal sample size of approximately **45** patients would easily afford at least a 0.804784 $1 - \beta$ level of statistical power to detect statistically significant RF/PEMF sample subgroup measurement differences observing a coefficient Alpha of 0.05 two-tailed level of significance. This sample size is based on both a conservative 0.3 (i.e., *Medium*) Effect Size for RF/PEMF treatment and pre-post procedure Cutometer[®] face gross elasticity measurement differences reported in Krueger, et. al (2011).⁵

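### Four formal null hypotheses share one P<0.05 rule with no multiplicity control: about a 13–18.5% chance of at least one false significant result if all four nulls are true

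*Combined protocol and SAP*

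**What the plan says.** Section 10.2 opens with "Statistical null hypothesis for primary endpoint: there will be no statistical change in gross elasticity" and continues in the same form for each secondary endpoint, starting with "Statistical null hypothesis for secondary endpoint #1: there will be no statistical change in the FWES". GAIS and subject satisfaction each have their own null as well, so there are four in all.

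Section 10.4.1 closes with one threshold: a P-"value of <0.05 will be considered statistically significant". Section 10.5 uses an "Alpha of 0.05 two-tailed level of significance". Section 10.4.8 adds: "For all endpoints, additional sub-group analysis may be performed based on age group and Fitzpatrick skin type". Section 10.4.9, the place for a multiplicity strategy, reads in full "Not applicable".

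On hierarchy, 4.2.1 names one primary endpoint, the change in gross elasticity (R2), and 4.2.2 gives the three secondaries a supporting role. On visits:

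- **R2:** 4.2.1 sets baseline against one late reading. Sections 7.1.1 and 7.3.7 also schedule week 7, and 10.4.1 and 10.5 work with three time points.
- **FWES:** 4.2.2 uses week 20 only and 10.4.3 treats it as one endpoint. The synopsis lists weeks 7 and 20.
- **GAIS:** weeks 7 and 20, called a repeated measure in 10.4.3.
- **Satisfaction:** weeks 4, 7 and 20, also called a repeated measure.

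**The concern.** Multiplicity does apply to a plan that writes four null hypotheses and one unadjusted threshold. The 5% level in 10.4.1 and 10.5 describes a single test, not the set of significance claims that the plan leaves open. Nothing stops a null week 20 elasticity result from being reported beside, or overshadowed by, a nominally significant week 7 reading or subject-rated scale.

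Two features add to this. Section 10.1 leaves the analysis plan to be finalised after data collection ends, in an open-label study, so the choice of visit or endpoint to stress is not closed beforehand. And there is no lower tier for supportive results: 4.2.3 lists no exploratory endpoints and 10.4.11 no exploratory analyses.

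**Working it through.** **The plan's own figures.** The documents give no family-wise error rate to reproduce. The stated figures nearby are alpha 0.05 and power 0.804784 at about 45 patients with effect size 0.3 (10.5). The power could not be confirmed, because 10.5 omits the test family, the type of effect size and the within-subject correlation. At N = 45, a two-sided paired t-test with standardised mean change 0.3 gives 0.503; a within-subject repeated-measures ANOVA with f = 0.3 and three measurements gives 0.876 at correlation 0 and 0.994 at 0.5. The error-rate calculation does not depend on this figure, but the fix does.

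**Inputs.** Alpha per test 0.05, two-sided (10.4.1, 10.5). Four nulls (10.2). Follow-up readings: R2 2, FWES 1, GAIS 2, satisfaction 3 (7.1.1, 4.2.2), so 2 + 1 + 2 + 3 = 8 visit-level contrasts. The correlation between test statistics is not given; it is assumed common to all pairs and varied from 0 to 0.7.

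**Formula.** With k independent tests and every null true, P(at least one P<0.05) = 1 − 0.95^k.

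- k = 1: 5%
- k = 2: 1 − 0.9025 = 9.75%
- k = 4: 1 − 0.8145 = 18.5%
- k = 8: 1 − 0.6634 = 33.7%

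For correlated tests, the same probability was simulated with equicorrelated two-sided z-tests (1,000,000 draws):

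| Assumed correlation | 4 tests, one per hypothesis | 8 tests, one per visit |
|---|---|---|
| 0 | 18.5% | 33.7% |
| 0.3 | 17.4% | 30.0% |
| 0.5 | 15.5% | 25.1% |
| 0.7 | 13.0% | 19.1% |

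If FWES were also tested at week 7, as the synopsis allows, there would be nine contrasts and 37.0% under independence. Subgroup tests are optional and undefined in number, so they are not counted.

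**The primary alone.** One fixed visit keeps 5%. If a significant change at either week 7 or week 20 would count, k = 2 and the error is up to 9.75%. Positive correlation between two readings on the same women would lower it.

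**Possible remedies.** Bonferroni over four hypotheses uses 0.05/4 = 0.0125 each and gives 1 − 0.9875^4 = 4.9% under independence. At N = 45, for an effect with about 80% power in a paired t-test at 0.05 (standardised mean change about 0.43), it cuts power on the primary to about 60%. A fixed sequence starting with the primary holds family-wise error at or below 5% and leaves the primary at 0.05.

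**The case against.** The strongest reply is that the hierarchy already exists: 4.2.1 names one primary and 4.2.2 makes the secondaries supportive, so the main claim is a single test at 5%. That stands for a primary test fixed at one visit. It does not cover the whole plan, because the visit is not fixed consistently, and a supportive role is not a descriptive label when each secondary has its own null hypothesis.

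A reader might go further and infer that the trial's main claim carries a false-positive risk of up to a third. The documents do not support that. The figure of about 34% is the chance of any false positive anywhere in the family, with every null true and eight separate, independent tests. Sections 10.4.1 to 10.4.3 speak of GEE models, ANOVA and repeated measures; none specifies a test at each visit, and readings on the same women are unlikely to be independent.

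The reach of the threshold is also partly inference. The P<0.05 sentence ends a paragraph about elasticity models, and 10.4.3 names no test or threshold for any secondary. Reading it as the general rule is reasonable, since it stands under the general approach and no other rule is given, but this is not explicit.

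Finally, some of the counted tests are not well defined. Neither 7.1.1 nor the table in 7.3.7 schedules GAIS or satisfaction at baseline, although the synopsis speaks of satisfaction questionnaires before treatment. The change nulls for these two scales cannot be tested clearly as written, so the remedy must give GAIS a reference value and cannot test a change in satisfaction.

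**Conclusion.** The point holds, with a limited size. With one test per written hypothesis and all nulls true, the chance of at least one false significant result is about 13–18.5% (assumed correlation 0.7 to 0) against the nominal 5%. The range of about 19–34% applies only if all eight visit-level contrasts are tested separately. The primary stays at 5% if its visit is fixed and can reach 9.75% if either follow-up visit may carry the claim. All of this rests on reading 10.4.1 as the rule for all four hypotheses and on assumed correlations. It is a matter the sponsor should settle in the SAP; it does not show that a single pre-fixed primary test would be invalid.

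**What to change.** Replace the entry in 10.4.9 with wording such as:

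> The change in R2 from baseline to week 20 (as in 4.2.1) is the only primary test, two-sided 0.05. If it is significant, FWES change at week 20 and then GAIS at week 20 (against 0, no change) are tested at 0.05 in that order, stopping at the first non-significant result. Satisfaction (no baseline scheduled), week 4, week 7 and subgroup results are reported as estimates with 95% CI, without significance claims.

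Here week 20 means the Visit 9 reading, the only Cutometer reading scheduled after week 7. Taking 0 as no change assumes that the midpoint of the −3 to 3 GAIS scale has that meaning, and the SAP should say so. The order of FWES before GAIS is a choice; the sponsor may prefer another. A simpler alternative, equally in keeping with 4.2.2, is to label all secondary P-values descriptive. Either way, 10.2 should be brought into line, and the change made before outcome data are examined rather than at the late finalisation that 10.1 allows.

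The cost is wording, with no added patients or visits, but it is not free. A secondary may lose a significance claim. The power statement in 10.5 is written for three time points and must be restated for the chosen primary contrast; unchanged power cannot be promised, since a two-sided paired test with standardised change 0.3 would have only about 50% power at N = 45.
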